14.2 Primary and Secondary Efficacy Endpoints

For the primary efficacy endpoint at Week 52 (ie, the change in the hFVIII activity during Weeks 49-52 post-BMN 270 infusion from baseline, as measured by one-stage clotting assay), a one-sample t-test will be used to test the null hypothesis that the change is 0 or less against the alternative hypothesis that the change is greater than 0. Descriptive summaries of the proportions of subjects whose FVIII activity during Weeks 49-52 is greater than or equal to select thresholds, such as 15, 25 and 30 IU/dL, and the confidence intervals of the proportions will also be provided. The FVIII activity as measured by chromogenic assay will be analyzed similarly, as a supportive analysis.

For the first secondary efficacy endpoint at Week 52 (ie, the change in the annualized utilization (IU/kg) of exogenous FVIII replacement therapy during Weeks 5-52 post-BMN 270 infusion from baseline), a one-sample t-test will be performed to test the null hypothesis that the change is 0 or greater against the alternative hypothesis that the change is less than 0.

For the second secondary efficacy endpoint at Week 52 (ie, the change in ABR, annualized bleeding rate, during Weeks 5-52 post-BMN 270 infusion from baseline), a one-sample t-test will be performed to test for non-inferiority of BMN 270 against FVIII prophylaxis (ie, the baseline ABR calculated using subjects' historical medical records during the year prior to enrollment) using a margin of 3.5, ie, to test the null hypothesis that the change is 3.5 or greater against the alternative hypothesis that the change is less than 3.5. If non-inferiority is demonstrated, the test for superiority of BMN 270 against FVIII prophylaxis will be performed. The primary analysis of this endpoint is planned to be performed pooling all 70 enrolled subjects, assuming the baseline ABR of the first enrolled 20 subjects (whose baseline data is entirely based on historical medical records) and the baseline ABR of the later enrolled 50 subjects (whose baseline data is based on both data from historical medical records and data collected during study BMN 270-902) are similar. The poolability will be

Page 101

examined by comparing the corresponding baseline ABRs. Details will be provided in the statistical analysis plan.

The primary and secondary efficacy hypotheses will be tested hierarchically according to the order described above. Multiple comparison procedures are described in greater detail in the following.

As described in Section 14.1.1, an interim analysis is planned after 20 treated subjects have completed the Week 26 visit (or have discontinued study participation prior to Week 26).

For controlling the probability of a Type I error for the interim and final analyses of the primary efficacy endpoint, the Hochberg procedure will be used. That is, if both the interim and final p-values are ≤ 0.05 , then both are declared statistically significant; otherwise, if either p-value is ≤ 0.025 , then that result is significant. (All p-values are 2-sided.) Since the final analysis results are not available at the time of the interim analysis, the procedure will be implemented as follows.

- If $p \le 0.025$ at the interim analysis, then the interim result is declared significant and the final analysis is carried out at the 0.05 level.
- If $0.025 at the interim analysis, then the final analysis is carried out at the 0.05 level. However, the significance of the interim result cannot be established at the time of the interim analysis; if <math>p \le 0.05$ for the final analysis, then both the interim and final analyses are declared significant, but if p > 0.05 for the final analysis, then neither the interim nor the final analysis is declared significant.
- If p > 0.05 at the interim analysis, then the interim analysis is not declared significant, and the final analysis is carried out at the 0.025 level.

Regardless of the interim analysis results, the study will continue to completion and the final analysis will be performed at Week 52.

For controlling the probability of a Type I error for the primary and secondary efficacy endpoints at the final analysis, a hierarchical (sequential) multiple comparison procedure will be used, after applying the truncated Hochberg procedure for parallel gatekeeping. Specifically:

- If both the interim and final results are significant (as described above), then at the final analysis the primary and secondary endpoints will be tested hierarchically using alpha = 0.05.
- If either the interim or the final result, but not both, is significant, then at the final analysis the primary and secondary endpoints will be tested hierarchically using alpha = 0.025.

Page 102

If neither the interim nor the final result is significant, then at the final analysis the secondary endpoints will not be tested.

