14.1.1 Interim Analyses

An interim analysis is planned after 20 treated subjects have completed the Week 26 visit (or have discontinued study participation prior to Week 26).

The primary efficacy endpoint for the interim analysis is change in the hFVIII activity, as measured by one-stage clotting assay, during Weeks 23-26 post-BMN 270 infusion from baseline. Each subject's hFVIII activity during Weeks 23-26 is defined as the median of the values obtained during this 4-week window. Values for hFVIII activity will be excluded if obtained within 72 hours since the last infusion of exogenous FVIII protein concentrates. A 2-sided one-sample t-test will be used to test the null hypothesis that the change is 0 or less against the alternative hypothesis that the change is greater than 0. In addition, subjects' hFVIII activity post-Week 23, defined as the median of the values obtained from Week 23 to the time of last follow-up, will be analyzed similarly as an important sensitivity analysis, utilizing additional data beyond Week 26. Descriptive summaries of the proportions of subjects whose FVIII activity during Weeks 23-26 and from Week 23 to the time of last follow-up is greater than or equal to select thresholds, such as 15, 25 and 30 IU/dL, and the confidence intervals of the proportions will be provided, respectively. The FVIII activity as measured by chromogenic assay will be analyzed similarly, as a supportive analysis.

The Hochberg procedure will be used to adjust for multiplicity of the interim analysis at Week 26 and the final analysis at Week 52 of the primary efficacy endpoint. (Regardless of the interim analysis results, the study will continue and the final analysis will be performed at Week 52.) At the final analysis at Week 52, the secondary efficacy endpoints will be tested hierarchically; the level of significance will be determined by the truncated Hochberg procedure for parallel gatekeeping. These multiple comparison procedures are described in greater detail in Section 14.2.

The secondary and tertiary endpoints will be summarized descriptively at the interim (Week 26) analysis.

Page 100

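### Amendment 1, Section 14.2: untruncated Hochberg cut-offs are paired with a 0.025 carry-over to the secondaries, so worst-case familywise error reaches 7.4%, not 5%

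*Protocol*

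**What the plan says.** In Amendment 1 the interim analysis (20 treated subjects, FVIII activity at Weeks 23-26) and the final analysis (Weeks 49-52) each carry a test of the primary endpoint. Section 14.2 treats the two as a Hochberg pair. Its first step reads: "if both the interim and final p-values are ≤ 0.05 , then both are declared statistically significant". When that condition is not met, a second step looks at each result singly: "otherwise, if either p-value is ≤ 0.025 , then that result is significant". On sidedness the section notes: "All p-values are 2-sided".

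The rule is then set out in order of time. After an interim p of 0.025 or less, "then the interim result is declared significant and the final analysis is carried out at the 0.05 level". After an interim p above 0.05, "then the interim analysis is not declared significant, and the final analysis is carried out at the 0.025 level". In between, the interim result waits for the final one.

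For the secondary endpoints, Section 14.1.1 and the synopsis say that "the level of significance will be determined by the truncated Hochberg procedure for parallel gatekeeping". Section 14.2 gives the levels: 0.05 if both results are significant, no secondary testing if neither is, and for the mixed case ("If either the interim or the final result, but not both, is significant") a hierarchy at 0.025. No truncation fraction is given anywhere in the amendment.

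**The concern.** Ordinary Hochberg spends the whole 0.05 inside the interim/final pair. If only one member is rejected, the other may still be a true null on which the full 0.05 has been risked, so nothing remains for the secondaries. Truncation exists to hold some alpha back for that case, and it pays for this with a stricter cut-off for the larger p-value. The printed rule takes the lenient cut-off of the untruncated version and the generous carry-over of the fully truncated one.

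What is at stake is strong control of the familywise error over the interim claim, the Week 52 primary claim and the secondary claims (FVIII use, then ABR). This is not detail left to the SAP, because the levels are fully fixed in the protocol text.

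**Working it through.** **Inputs** (Amendment 1, Sections 14.1.1, 14.2 and 14.6): cut-offs 0.05 (both) and 0.025 (one); carry-over 0.05, 0.025 or 0 after two, one or no rejections; two-sided p-values; n = 70 and effect size 0.6 for the final primary test at 0.025.

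**1. The plan's own figures.**
- For two independent true nulls the printed Hochberg pair has error 0.05^2 + 2 x 0.025 x 0.95 = 0.0025 + 0.0475 = 0.0500. The pair taken alone is sound.
- A one-sample t-test with n = 70, effect size 0.6 and two-sided 0.025 has power 99.6%, consistent with the stated minimum of 95%.

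**2. What a truncated Hochberg pair allows.** With fraction g and alpha = 0.05:
- larger p-value: cut-off (1+g)/2 x 0.05;
- smaller p-value: cut-off 0.025 for every g;
- carry-over after exactly one rejection: (1-g)/2 x 0.05.

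| g | Cut-off, larger p | Carry-over after one rejection | Error in the configuration of step 3 |
|---|---|---|---|
| 0 | 0.025 | 0.025 | 4.94% |
| 0.5 | 0.0375 | 0.0125 | 4.95% |
| 1 | 0.05 | 0 | 5.00% |
| As printed | 0.05 | 0.025 | 7.38% |

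**3. Worst case.** Take the interim null as true, the Week 52 effect as real with power near 1, the first secondary null as true, and the tests as independent. Because the final p-value is small, the interim is falsely declared whenever its p is 0.05 or less, which has probability 0.05. In the other 0.95 only the final is significant and the secondary is tested at 0.025. So

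FWER = 0.05 + 0.95 x 0.025 = 0.05 + 0.02375 = 0.07375, or 7.4%.

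**4. Sensitivity** (simulation, 4 million draws per setting).
- At the protocol's effect size, with non-centrality 0.6 x sqrt(70) = 5.02: 7.38%.
- With a weaker final effect the excess shrinks: 6.7% at non-centrality 3.24 and 6.2% at 2.8.
- With correlated tests the shared 20 of 70 subjects limit the interim/final correlation to sqrt(20/70) = 0.53. As the assumed subject-level correlation rises from 0 to 0.95 the error falls from 7.4% to 6.9% (7.1% at 0.8).
- Counting only false claims in the favourable direction: about 3.7% against 2.5%.

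**5. Other configurations.**
- All nulls true: 5.0% or less.
- Only the secondary null true: 5.0%.
- Interim effect real, Week 52 null true: 7.4% under independence if the secondaries are tested after an interim-only success, but 5.0% if the failed Week 52 primary stops the hierarchy. Section 14.2 can be read either way. It says the primary and secondary endpoints are tested in hierarchy, which implies a stop, yet it bars secondary testing outright only when neither result is significant.

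**The case against.** **The configuration is remote.** For a one-time infusion, no effect at Weeks 23-26 with a large one at Weeks 49-52 is hard to picture, and Amendment 1 justifies its early interim by FVIII levels that stayed up from before Week 26 to after Week 52. This stands as a limit on practical weight. It does not rescue the procedure, since strong control has to hold in every configuration.

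**The faulty branch is common.** A reader might infer frequent inflation, because the 20-subject interim has only 72% power at 0.05 with effect size 0.6, so that about 28% of trials reach the mixed case. That inference fails: it assumes a real interim effect, so no false interim claim is possible. With a null secondary, independence and final power near 1 the error there is 0.72 x 0.05 + 0.28 x 0.025 = 4.3%.

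**The secondary claims themselves are inflated.** A reader might infer this too. In the worst case the first secondary's own false-positive rate is 0.05 x 0.05 + 0.95 x 0.025 = 2.6%. Five of the 7.4 points are the false interim claim. The excess lies in the union of the two.

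**The promise of control is narrower.** Section 14.2 promises control for the primary and secondary endpoints at the final analysis and treats the interim/final pair in a separate sentence. For the Week 52 primary and secondaries alone, with a failed primary stopping the hierarchy, the error is at most 5%. Likewise, if interim and final were one hypothesis, the total would stay within 5%. But Section 14.1.1 gives the interim its own endpoint window, Section 14.2 gives it its own declaration of significance, and parallel gatekeeping is by its nature a procedure for the combined family.

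**The text is superseded.** This stands as a limit on scope. Amendment 2 follows in the file, but the part shown ends before its statistical section. The note to file describes version 7.0 as making ABR the primary endpoint, with a hierarchy at alpha 0.0498.

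**Conclusion.** The inconsistency is real. As written in Amendment 1, the cut-offs and the carry-over belong to two different truncation fractions, and the procedure does not hold 5% over the interim, Week 52 primary and secondary claims. The error is up to 7.4% two-sided, or about 3.7% against 2.5% for favourable claims.

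That figure is a worst case. It rests on interim and final being separate hypotheses, a true interim null, a real Week 52 effect with power near 1, a true first secondary null, and independence. High correlation lowers it to about 6.9-7.1%. It is not the error rate in every configuration, and with all nulls true, or only the secondary null true, the rule keeps to 5%.

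The handling of the secondaries after an interim-only success is an ambiguity of wording, not a plain instruction to test them regardless. Nor do the documents support reading this as a flaw in the 2-year analysis, which followed a later version.

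**What to change.** Use one truncation fraction throughout Sections 14.1.1 and 14.2 and the synopsis, wherever a later version retained the rule. The simplest choice is fraction 0:
- test the interim and the final primary each at two-sided 0.025;
- pass 0.025 to the secondaries after one rejection and 0.05 after two;
- state that no secondary is tested if the Week 52 primary fails.

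The worst-case familywise error is then 0.025 + 0.975 x 0.025 = 4.94% with a true interim null, and at most 5.0% when only the secondary null is true. Fraction 0.5 (0.0375 for the larger p, 0.025 for the smaller, carry-over 0.0125) is also coherent, at 4.95%.

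The cost is wording plus a stricter cut-off for the larger p-value: an interim p between 0.025 and 0.05 can no longer become significant later, and the final test is always at 0.025. Section 14.6 already sizes the study at 0.025, and the final primary test keeps 99.6% power with n = 70 and effect size 0.6, so the sample size need not change.

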14.3 Immunogenicity

Analysis of total and neutralizing antibody response and other immunological parameters will be primarily descriptive and involve both inter-subject and intra-subject comparisons.

14.4 Pharmacodynamic Analyses

Plasma FVIII protein concentrations and FVIII activities determined over the course of the study will primarily be evaluated and summarized with descriptive statistical measures (eg, mean, standard deviation, CV%, min, median, max).

14.5 Safety Analysis

The Medical Dictionary for Regulatory Activities terminology (MedDRA) will be used by the Sponsor to assign system organ class and preferred term classification to events and diseases, based on the original terms entered on the eCRF.

All AEs will be coded using the current version of MedDRA. The incidence of AEs will be summarized by system organ class, preferred term, relationship to study drug, and severity. A by-subject listing will be provided for those subjects who experience a serious AE (SAE), including death, or experience an AE associated with early withdrawal from the study or study drug.

Clinical laboratory data will be summarized by the type of laboratory test. For each clinical laboratory test, descriptive statistics will be provided on Baseline as well as all subsequent visits. Descriptive statistics for physical examination results and vital signs will also be provided.

Detailed statistical methods will be provided in the SAP.

14.6 Determination of Sample Size

Seventy (70) subjects may be dosed in the study. The sample size for this study is based on clinical and statistical considerations in order to provide sufficient data to assess both safety and efficacy of BMN 270.

A sample size of 70 will provide at least 95% power to demonstrate that the change in hFVIII activity during Weeks 49-52 from baseline is greater than 0, assuming an effect size of 0.6, using a one-sample t-test with a 2-sided significance level of 0.025.

Page 103

A sample size of 70 will provide at least 95% power to demonstrate that the change in the annualized utilization (IU/kg) of exogenous FVIII replacement therapy during Week 5 to Week 52 post-BMN 270 infusion from the baseline is less than 0, assuming an effect size of 0.6, using one-sample t-test with a 2-sided significance level of 0.025.

A sample size of 70 will also have at least 95% power to demonstrate that the change in the annualized number of bleeding episodes requiring exogenous FVIII replacement treatment (ABR) during Week 5 to Week 52 of the study post-BMN 270 infusion from the baseline ABR is less than 3.5 (non-inferiority margin), assuming the pre- and post-BMN 270 infusion population mean ABRs are 3.5 and 1 respectively, using a one-sample t-test with a 2-sided significance level of 0.025. Under the same assumptions, a sample size of 70 will have approximately 90% power to demonstrate that the change is less than 0, i.e. superiority of BMN 270 against FVIII prophylaxis.

Overall, a sample size of 70 will have greater than 80% power for testing the primary and secondary efficacy endpoints hierarchically at the final analysis with a 2-sided significance level of 0.025.

14.7 Analysis Populations

The efficacy analysis set will consist of all subjects who receive the BMN 270 infusion.

The safety population is the same as the efficacy analysis set.

14.8 Changes in the Conduct of the Study or Planned Analyses

Only BioMarin may modify the protocol. Any change in study conduct considered necessary by the Investigator will be made only after consultation with BioMarin, who will then issue a formal protocol amendment to implement the change. The only exception is when an Investigator considers that a subject's safety is compromised without immediate action. In these circumstances, immediate approval of the chairman of the IRB/IEC/REB must be sought, and the Investigator should inform BioMarin and the full IRB/IEC/REB within 2 working days after the emergency occurs.

With the exception of minor administrative or typographical changes, the IRB/IEC/REB must review and approve all protocol amendments. Protocol amendments that have an impact on subject risk or the study objectives, or require revision of the ICF, must receive approval from the IRB/IEC/REB prior to their implementation.

When a protocol amendment substantially alters the study design or the potential risks or burden to subjects, the ICF will be amended and approved by BioMarin and the IRB/IEC/REB, and all active subjects must again provide informed consent.

Page 104

15 DATA MONITORING COMMITTEE

An independent DMC will be convened for this study. The duties of the DMC will include:

- Conducting an ongoing review of individual subject safety and efficacy data during the study.
- Recommending whether to enroll subjects at a different dose level (not to exceed 6E13 vg/kg) based on emerging data from 270-301 and the overall risk/benefit analysis of BMN 270.
- Reviewing ongoing safety and efficacy data for comparability of drug manufacturing lots within 270-301 and between 270-201 and 270-301.
- Making other recommendations on the conduct and reporting of the trial based on their evaluation of clinical data.

Details on the composition of the committee, frequency of meetings, and other committee functions and parameters are included in the DMC Charter and in the Statistical Analysis Plan (SAP).

Page 105

16 COSTS, COMPENSATION, AND SUBJECT INJURY

There will be no charge to study subjects to be in this study. BioMarin will pay all costs of tests, procedures, and treatments that are part of this study. In addition, after IRB/IEC/REB approval, BioMarin may reimburse the reasonable cost of travel for study-related visits in accordance with BioMarin's travel and reimbursement policy. BioMarin will not pay for any hospitalizations, tests, or treatments for medical problems of any sort related solely to the study subject's disease. Costs associated with such hospitalizations, tests, and treatments should be billed and collected in the way that such costs are usually billed and collected outside the study.

The Investigator should contact BioMarin immediately upon notification that a study subject has been injured by the study drug or by procedures performed as part of the study. Any subject who experiences a study-related injury should be instructed by the Investigator to seek immediate medical treatment at a pre-specified medical institution if possible, or at the closest medical treatment facility if necessary. The subject should be given the name of a person to contact to seek further information about, and assistance with, treatment for study-related injuries. The treating physician should bill the subject's health insurance company or other third party payer for the cost of this medical treatment. If the cost of the medical treatment is not covered by health insurance or another third party that usually pays these costs, then either BioMarin or the institution may pay for reasonable and necessary medical services to treat the injuries caused by the study drug or study procedures. In some jurisdictions, BioMarin is obligated by law to pay for study-related injuries without prior recourse to third party payer billing and/or regardless of fault. If this is the case, BioMarin will comply with the law.

Page 106

17 CASE REPORT FORMS AND SOURCE DOCUMENTS

Electronic case report forms will be provided for each subject. The Investigator must review and electronically sign the completed eCRF casebook to verify its accuracy.

eCRFs must be completed using a web-based application developed and validated. Study site personnel will be trained on the application and will enter the clinical data from source documentation. Unless explicitly allowed in the eCRF instructions, blank data fields are not acceptable.

In the event of an entry error, or if new information becomes available, the value will be corrected by deselecting the erroneous response and then selecting or entering the factual response. In compliance with ICH GCP Guidelines and 21 CFR Part 11, the system will require the personnel making the correction to enter a reason for changing the value. The documented audit trail will include the reason for the change, the original value, the new value, the time of the correction and the identity of the operator.

BioMarin's policy is that study data on the eCRFs must be verifiable to the source data, which necessitates access to all original recordings, laboratory reports, and subject records. In addition, all source data should be attributable (signed and dated). The Investigator must therefore agree to allow direct access to all source data. Subjects must also allow access to their medical records, and subjects will be informed of this and will confirm their agreement when giving informed consent. If direct source document verification of study data by the site monitor is prohibited by institutional policy or local law, then the Investigator must make available facilities and/or personnel to allow GCP-compliant source verification to occur. Examples of such methods include certified copies of records which have study data visible but sensitive information redacted, or other GCP-compliant means agreed between the Investigator and the Sponsor.

A site monitor designated by BioMarin will compare the eCRFs with the original source documents at the study site and evaluate them for completeness and accuracy before designating them as "Source Data Verified" (SDV). If an error is discovered at any time or a clarification is needed, the site monitor, or designee, will create an electronic query on the associated field. Site personnel will then answer the query by either correcting the data or responding to the query. The site monitor will then review the response and determine either to close the query or re—query the site if the response does not fully address the question. This process is repeated until all open queries have been answered and closed.

Before a subject's eCRF casebook can be locked, data fields must be source data verified and all queries closed. Refer to the Study Monitoring Plan for details on which fields must be

Page 107

source data verified. The Investigator will then electronically sign the casebook, specifying that the information on the eCRFs is accurate and complete. The Data Manager, or designee, will then set the status of the forms, visits, and the entire casebook to Locked. Upon completion of the CSR, an electronic copy of each site's casebooks will be copied to a compact disk (CD) and sent to each site for retention with other study documents.

Page 108

